time points: (1) before induction of anesthesia, (2) when awake in the PACU, (3) just before, and (4) 30-60 mins after receiving analgesic or antiemetic therapy and (5) just before discharge home. The order of presentation of scales will be randomized but the same for all time points for an individual subject. After the first set of assessments are done in the PACU, patients will also be asked to rate their nausea on a 5 point Likert scale as : (1) Much worse than before, (2) A little worse than before, (3) The same as before (4) A little better than before and (5) Much better than before. They will also be asked if they want any treatment of their nausea. Another set of assessments will be just prior to discharge. All other aspects of patient management will be the standard care given to such children at the Texas Children's Hospital. Patients will be discharged from the PACU when they have achieved the standard criteria set for discharge at the TCH. At the time of discharge we will give the parents a diary to record the the MAXIMUM nausea on the VAS and BARF scales and mail it back in a stamped envelope. We will phone them about 24 hours after surgery and ask if the child had any nausea, vomiting and what medications were used after going home. We will ask the parent to rate their satisfaction with the control of nausea and with the entire perioperative experience on a 0-10 scale. We will remind them to mail the nausea assessments back and to state which face represented the maximum nausea after discharge.

Section G: Sample Size/Data Analysis

G1. Sample Size

How many subjects (or specimens, or charts) will be used in this study?

Local: 387 Worldwide: 387

Please indicate why you chose the sample size proposed:

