The study has a number of aims and the power analysis is provided separately for each aim: (1) In order to examine the age related ability to use the BARF scale we will recruit 28 subjects each in the ages of 3, 4, 5, 6, 7, 8, 9, 10, 11, 12 and >12 years years (28 X 11 = 308). Power analysis was based on an alpha of 0.05, power of 80% and a large effect size (Cohen's d = 0.80) as it was assumed a large difference would be needed for the results to have clinical utility (Pain 2011; 152: 1327-33). This suggested a group size of 24 would be needed. Allowing for a drop out rate of 20% we plan to recruit 28 in each of the 11 groups. (2) Power analysis for minimum clinically relevant difference in BARF scores: A one face difference in the BARF scale is the minimum difference that can be detected. A previous study showed that the mean BARF scores in the postoperative period in children was 1.6 +/- 2.4 (Pediatrics. 2011 Jun;127(6):e1542-9) . In order to detect a 1 face difference with 80% power at the 0.05 level of significance we will need 93 subjects who had a change in their nausea scores. Assuming an incidence of postoperative nausea and vomiting (PONV) of 33% (which is similar to previous data in children), a group size of 93 X3= 279 will be required to obtain 93 subjects with a change in nausea scores. We plan to recruit 387 subjects to allow for a 35% dropout rate.

This sample size will have a >80% power for the other aims of the study (The BARF and VAS scores associated with a patient's perception of the need for treatment and the test - retest reliability of the VAS and BARF scores when nausea is rated as unchanged.)

G2. Data Analysis

Provide a description of your plan for data analysis. State the types of comparisons you plan (e.g. comparison of means, comparison of proportions, regressions, analysis of variance). Which is the PRIMARY comparison/analysis? How will the analyses proposed relate to the primary purposes of your study?

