Statistical Analysis: (1) The mean and SD of all scores will be calculated along with their distribution. The incidence of postoperative nausea and postoperative vomiting in the PACU and after discharge (post-discharge nausea) will be calculated. The incidence of severe nausea (score>6 on the BARF scale) and severe vomiting (3 or more episodes over 24 hours) will also be determined. (2) We will record the age of a child and their ability to rate their nausea on the BARF and VAS scales to determine the minimum age where a patient can reliably use the scale. (3) Changes in BARF and VAS nausea scores will be calculated for subjects who report their nausea as a little worse than before or a little better than before, to determine the minimum change in scores of clinical relevance. (4) The BARF score and its relationship to the request for rescue antiemetics will be examined by a Spearman's rank correlation. (5) The relationship between the first and subsequent BARF and VAS nausea scores in patients who state their nausea is 'the same as before?' will be examined by a Spearman's rank correlation and a Cronbach's alpha calculation. This will provide the test ? retest reliability.

Section H: Potential Risks/Discomforts

Describe and assess any potential risks/discomforts; (physical, psychological, social, legal, or other) and assess the likelihood and seriousness of such risks:

The risks are limited to possible loss of confidentiality as there are no changes in surgical or anesthetic management of the child other than obtaining data on estimating the degree of nausea. Loss of confidentiality is unlikely in view of standard steps taken to avoid this.

Section I: Potential Benefits

Describe potential benefit(s) to be gained by the individual subject as a result of participating in the planned work.

Subjects will not have any direct immediate benefits from participating in these studies.

Describe potential benefit(s) to society of the planned work.

Determining the clinical utility of a faces pain scale will facilitate treatment and research into this clinically important realm of suffering for children of all ages. Future patients may benefit from having such a tool as it will permit clinicians to measure the symptom severity and then treat such patients

Do anticipated benefits outweigh potential risks? Discuss the risk-to-benefit ratio.

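### The age quota of 28 does not cover 20% dropout from the 24 the plan says it needs: 24/0.8 = 30, and 28 leaves about 22

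*Combined protocol and SAP*

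**What the plan says.** G1 (Sample Size), aim 1, sets a quota for each single year of age from 3 to 12 and one for those over 12: 11 groups of 28, 308 in total. The stated basis is an "alpha of 0.05, power of 80% and a large effect size (Cohen's d = 0.80"). The text continues: "This suggested a group size of 24 would be needed. Allowing for a drop out rate of 20% we plan to recruit 28" per group. It gives neither the test nor its sidedness.

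G2 (Data Analysis), item 2, is the matching analysis: "We will record the age of a child and their ability to rate their nausea on the BARF and VAS scales", with the aim of finding the youngest age at which the scales can be used reliably. It names no comparison between ages.

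Total enrolment comes from aim 2, the minimum clinically relevant difference: "We plan to recruit 387 subjects to allow for a 35% dropout rate". The enrolment line agrees ("Local: 387 Worldwide: 387"). No age split is given for the recruits beyond 308.

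**The concern.** A dropout allowance should leave the required number once the expected loss has occurred. Here the required number, the loss rate and the quota are given together, and they do not fit: 20% off 28 falls below 24.

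Age-related reliability is objective 2 in Section D. A minimum usable age depends on the information at each single year of age, so the quota per age, rather than the overall total, has to carry this aim. If the quota is short, the 80% power claimed for the aim is not secured by the number chosen to secure it.

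**Working it through.** **Inputs, all from G1 aim 1 unless noted:** alpha 0.05; power 80%; d = 0.80; 24 needed per group; 20% dropout; 28 recruited in each of 11 groups. From G1 aim 2: 387 in total, 35% dropout.

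**1. The dropout step. This needs no assumption about the test.**
- Recruits needed = n/(1 − dropout) = 24/0.80 = 30; over 11 groups, 330.
- Adding 20% to 24, a common but incorrect shortcut, gives 24 × 1.2 = 28.8, so 29. The plan's 28 is reached only by rounding that down.
- Retained from 28: 28 × 0.80 = 22.4.
- Loss that 28 can absorb: 1 − 24/28 = 14.3%.
- If each child drops out independently with probability 20%, a group of 28 keeps at least 24 with probability about 31% (binomial).

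**2. Where the 24 comes from.** A two-sided comparison of two age groups is assumed, as the closest fit.
- Normal approximation: n = 2(1.960 + 0.842)²/0.80² = 24.53, so 25 per group.
- Two-sample t-test: 25.52, so 26 per group.
- One-sided, normal approximation: 19.3, so 20. A one-sided test does not explain 24.

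The plan's 24 is thus one or two below the two-sided answer. With 20% dropout, 25 needs 25/0.8 = 31.25, so 32 recruits (352 in total); 26 needs 26/0.8 = 32.5, so 33 (363 in total).

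**3. Power at the numbers retained.** One unadjusted pairwise comparison, d = 0.80, two-sided 0.05. The normal approximation is Φ(d√(n/2) − 1.960). For n = 22: 0.80 × √11 = 2.653; 2.653 − 1.960 = 0.693; Φ(0.693) = 75.6%.

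| Evaluable per group | t-test | Normal |
|---|---|---|
| 22 | 73.6% | 75.6% |
| 24 | 77.4% | 79.1% |
| 25 | 79.1% | 80.7% |
| 26 | 80.7% | 82.2% |
| 28 | 83.6% | 84.9% |

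**4. What the total of 387 could do.**
- Beyond the quotas: 387 − 308 = 79.
- Spread evenly: 387/11 = 35.2, so 35 per group (35 × 11 = 385).
- At 20% loss, 35 leaves 28. At 35% loss it leaves 22.75, with power 75.1% (t-test) or 77.0% (normal).
- Loss that 35 can absorb: 25.7% to keep 26, 28.6% to keep 25, 31.4% to keep 24.

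**The case against.** The strongest reply is that the study recruits 387, not 308. The 11 groups span the whole eligible age range, so the other 79 children must fall into them, and only 22 of the 79 are needed to bring every group to 30. Spread evenly, 387 leaves about 28 per group after 20% loss. This is right about capacity. But the only commitment per age is 28, and recruits come from the surgery schedule (J2), so nothing makes the extra children fall where they are needed. The figure of 22 is what the quota secures, not a forecast for every group.

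Second, the power loss rests on a test that the plan does not state. On a one-sided t-test, 22 per group would give about 83%; a paired comparison within an age would need only 15. Neither reproduces 24, and the two-sided two-sample comparison comes closest. The power figures remain conditional on it; the dropout error does not.

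Third, a correction to 30 would satisfy the plan's own inputs, and the difference between 24 and 25 or 26 is small. That is fair. However, 24 retained gives 77–79% on the assumed test, so 30 repairs the dropout arithmetic without quite reaching 80%.

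Fourth, different dropout rates for the two aims are plausible, because the aims need different data. I accept this: the 20% and 35% do not contradict each other, and the difference only lacks an explanation.

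Last, 387 does not itself allow for 35% loss from the 279 that aim 2 requires: 279/0.65 = 429.2, so 430. If the total rose to 430, an even spread would give about 39 per group and cover the age aim at 20% loss. That would ease the problem, but a quota per age would still have to be stated.

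**Conclusion.** The concern holds. On the plan's own figures the age quota is 2 per group short (28 against 30; 308 against 330 in total), whatever test was intended. If a two-sided two-sample comparison is assumed, the quota is 4 to 5 short, and the 22 it retains give 74–76% power for one unadjusted pairwise comparison, about 4 to 6 points below the stated 80%. The effect is modest and can be repaired within the planned enrolment if dropout is about 20%. As written, 80% power is not guaranteed in each age group.

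**What to change.** - Set the age quota at 33 to 35 per group (363 to 385, within 387). At 20% dropout this leaves 26 to 28 and gives about 81–84% power by t-test for one unadjusted pairwise comparison. If the sponsor keeps 24 as the requirement, 30 is the least that is consistent with 20% dropout.
- Otherwise keep 28 and restate the power as about 74–76%, on the two-sided two-sample assumption.
- In either case, state the test and sidedness that produced 24 in G1, and name the matching age comparison in G2 item 2.
- Add a sentence on why the dropout rate is 20% for this aim and 35% for the next. If 35% applies here too, say that 35 per group leaves about 23 and about 75–77% power.

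The cost is wording and an age allocation for children already planned; no extra patients are needed. The drawback is that the scarcer ages may take longer to fill, and 35 per group leaves only 2 of the 387 places unallocated.

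### G1 uses 20% dropout for aim (1) and 35% for aim (2) without reconciling them, and at neither rate do 28 recruits per age group leave the 24 evaluable children tied to 80% power

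*Combined protocol and SAP*

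**What the plan says.** Section G1 gives a power analysis for each aim in turn.

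- **Aim (1), age-related ability to use the scale.** The inputs are alpha 0.05, power 80% and Cohen's d = 0.80. The result is: "This suggested a group size of 24 would be needed". Recruitment follows: "Allowing for a drop out rate of 20% we plan to recruit 28 in each of the 11 groups", which G1 totals as 308.
- **Aim (2), minimum clinically relevant difference.** With a 33% incidence of nausea and vomiting, "a group size of 93 X3= 279 will be required to obtain 93 subjects with a change in nausea scores". Recruitment follows: "We plan to recruit 387 subjects to allow for a 35% dropout rate".

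The study total is given as "Local: 387 Worldwide: 387". G1 does not define dropout for either aim, does not explain why the rates differ, and does not say how the 387 − 308 = 79 children beyond the age quotas are distributed by age. It names neither the test behind the 24 nor whether it is one- or two-sided.

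**The concern.** The same children, followed on the same rating schedule (F2), serve both aims. Two loss rates, 15 percentage points apart and without explanation, leave the reader unable to tell how many children per age group the investigators expect to analyse.

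This matters most for aim (1), whose groups are small. The 80% power rests on 24 evaluable children per group. If the quota does not deliver 24, the figure does not describe the plan as written. Age-related reliability is a stated objective (Section D), and G2 item (2) uses these data to find the youngest age at which the scale can be used reliably. Age groups smaller than intended would make a real difference between ages easier to miss.

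**Working it through.** **Inputs (G1):** alpha 0.05; power 80%; d = 0.80; 24 evaluable and 28 recruited per group; 11 groups; dropout 20% (aim 1) and 35% (aim 2); 279 needed before dropout for aim (2); total 387. **Assumption:** a two-sided two-sample comparison of means.

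**Reproducing the 24.** Normal approximation: n = 2(1.960 + 0.842)² / 0.80² = 24.5, so 25 per group. The t-test gives 25.5, so 26. The stated 24 is within two of both. One-sided versions give 20 (normal) and 21 (t), so the two-sided reading fits better. With n = 24, power is Φ(0.80 × √(24/2) − 1.960) = Φ(0.811) = 79.1% by normal approximation, and 77.4% by noncentral t.

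**Reproducing the 28.** 24 / (1 − 0.20) = 30; the common shortcut 24 × 1.20 = 28.8 gives 29. Recruiting 28 covers a loss of only 1 − 24/28 = 14.3%.

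**Evaluable children and power for aim (1)**, with power = Φ(0.80 × √(n/2) − 1.960) for the normal column and the noncentral t with 2n − 2 degrees of freedom for the t column:

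| Recruited per group | Loss | Evaluable n | Power (t) | Power (normal) |
|---|---|---|---|---|
| 28 (written quota) | 20% | 28 × 0.80 = 22.4 | 74.4% | 76.3% |
| 28 (written quota) | 35% | 28 × 0.65 = 18.2 | 65.0% | 67.5% |
| 387/11 = 35.2 (even spread, not stated) | 20% | 28.1 | about 84% | about 85% |
| 387/11 = 35.2 (even spread, not stated) | 35% | 22.9 | 75.4% | 77.2% |

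**Where the gap between 80% and 65% comes from (t-test).** From 80% to 77.4%, 2.6 points, is because 24 is slightly short by the t-test. From 77.4% to 74.4%, 3.0 points, is because 28 does not cover even 20% loss. From 74.4% to 65.0%, 9.4 points, is the move from 20% to 35% loss.

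**Recruitment that would leave 24.** At 20% loss: 30 per group, 30 × 11 = 330, which fits within 387. At 35% loss: 24 / 0.65 = 36.9, so 37 per group, 37 × 11 = 407, which does not.

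**Aim (2) total.** 279 / (1 − 0.35) = 429.2, so 430, and 279 × 1.35 = 376.7, so 377. The 387 matches neither and covers a loss of 1 − 279/387 = 27.9%. The total therefore does not show which loss rate was intended.

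**The case against.** **The rates may describe different losses.** A reader might infer that 20% and 35% contradict each other. The documents do not establish that. G1 sizes each aim separately, and the aims need different data. Aim (1) asks whether a child can produce a rating, and ratings begin before surgery in children who have passed the seriation task. Aim (2) needs an awake PACU rating, a later rating and a report of slight change. Heavier loss of paired postoperative data is plausible. G1 neither says nor excludes this. It has already allowed, through the 33% incidence step, for children whose nausea does not change, so the 35% comes on top of that and still needs a reason. The rates are unreconciled; they need not be incompatible.

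**The 65% is not the power of the study.** A reader might also take 65% as the power of the study as a whole. It applies to aim (1) only, and only if every age group stops at 28, which accounts for 308 of the 387 children. With an even spread of all 387, 35% loss leaves 22.9 per group, slightly more than the 22.4 that aim (1)'s own plan leaves at 20%. In that case the higher rate costs aim (1) nothing against its own quota, and at 20% loss power exceeds 80%. This objection stands as far as it goes. But the only age allocation G1 states is 28 per group, and recruitment from the surgery schedule (J2) does not ensure an even spread.

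**The test is assumed.** G2 item (2) describes recording age and ability to rate, with no two-group comparison. With a one-sided t-test, power would be about 84% at 22.4 evaluable and about 76% at 18.2. The percentages depend on the assumed test; the shortfall against G1's own 24 does not.

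**Conclusion.** The point holds in this form: the written quota of 28 leaves 22.4 or 18.2 evaluable children per age group at the two stated rates, and neither reaches the 24 on which the 80% rests. That comparison needs no assumption about the test.

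In power terms, under a two-sided two-sample t-test at d = 0.80, the quota gives about 74% at 20% loss and about 65% at 35%, against about 77% for 24 evaluable children. Only part of the distance from 80% is due to the dropout rate. If all 387 were spread evenly, the range would be about 75% to 84%, so 80% is attainable under one combination of assumptions that G1 does not state. The age allocation and the expected loss decide which figure applies, and G1 needs to give both. This is a correction to a stated figure that should be made; it does not call the design into question.

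**What to change.** In G1:

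1. Use one dropout rate for both aims, or keep two and tie each to a named loss with its reason (for example, no usable rating for aim (1), and no usable pair of postoperative ratings for aim (2)).
2. State how all 387 children are allocated across the 11 age groups, including the 79 beyond the quotas.
3. Name the test and its sidedness for aim (1), and replace 80% with the power at the chosen rate and allocation. Under the two-sided t-test this is about 74% (20%) or 65% (35%) for 28 per group, and about 84% (20%) or 75% (35%) for an even spread of 387.

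The cost is a rewording of G1. No extra enrolment is needed. The downside is that the stated power for aim (1) becomes less favourable, unless an even spread at 20% loss can be justified.

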Groups to be recruited will include:

Patients

Which if any of the following vulnerable populations will be recruited as subjects?

Children

Vulnerable populations require special protections. How will you obtain informed consent, protect subject confidentiality, and prevent undue coercion?

These are described in section J.

E3. Pregnant woman/fetus

Will pregnant women and/or fetuses (as described in 45 CFR 46 Subpart B) be enrolled in the research?

No

E4. Neonates

Will neonates of uncertain viability or nonviable neonates (as described in 45 CFR 46 Subpart B) be enrolled in the research?

No

E5. Children

Will children be enrolled in the research?

Yes

Section F: Design/Procedure

F1. Design

Select one category that most adequately describes your research:

d) Questionnaire/survey/interview

Discuss the research design including but not limited to such issues as: probability of group assignment, potential for subject to be randomized to placebo group, use of control subjects, etc.

The study design is a cross sectional study of patients undergoing surgery. There will be no group assignment, no placebo group and each patient will be his or her own control. Patients will receive standardized care according to the Attending Anesthesiologist's opinion of the clinical requirements for the specific situation. No changes in clinical practice or care of patients will occur solely for the purpose of the study. All patients will be asked to assess their pain and nausea using the visual analogue scales, the modified faces scale and the BARF scale as described below in the preoperative and postoperative areas. However, the order in which the scales are presented to the patient for assessment will be randomized to reduce the potential for an order effect where the patient choice of a response on one scale may influence the response on other scales. For example, having chosen a response two-thirds of the way up one scale, there will be a tendency to choose a response two-thirds of the way up the next scale.

Inclusion Criteria:

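### The 80% power in G1 (2) belongs to no analysis in G2 (3), which estimates a change in two smaller groups; state the expected precision instead

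*Combined protocol and SAP*

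**What the plan says.** Section G1 (2) sizes the study for the minimum clinically relevant difference in BARF scores. It takes one face as the target: "A one face difference in the BARF scale is the minimum difference that can be detected". Its only measure of spread comes from a cited study, in which the "mean BARF scores in the postoperative period in children was 1.6 +/- 2.4". It then gives the test conditions and the number together: "In order to detect a 1 face difference with 80% power at the 0.05 level of significance we will need 93 subjects who had a". The rest of that sentence limits the count to children whose nausea score moved. It names no test, no SD of change, no within-child correlation and no number of score points per face. The 93 is multiplied by 3 to give 279, and recruitment is set at 387.

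Section G2 (3) covers the same aim. It calculates BARF and VAS changes for children in two of the five answer categories, *a little worse* and *a little better*, "to determine the minimum change in scores of clinical relevance". It names no hypothesis, test, confidence interval or target precision. The only inferential statistics named in G2 are the Spearman correlations in items (4) and (5) and Cronbach's alpha in item (5).

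Section F1 describes the design as one in which "each patient will be his or her own control".

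**The concern.** Power belongs to a test. The aim here is to estimate a quantity, namely how far the score moves when a child calls the change small, and what matters for that is how narrow the confidence interval will be. G1 (2) gives a power figure for a test that G2 (3) does not contain, and gives no precision for the estimate that G2 (3) does produce.

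The two sections also count different children. G1 (2) counts everyone whose score changed. G2 (3) uses only the two *a little* answers; children who answer *much worse* or *much better* are set aside, and the rest are divided by direction. A reader who takes the 80% as covering this aim will expect more precision than the plan can promise. The chain from 93 to 279 to 387 fixes the study size, so this is the paragraph on which that reader would rely.

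**Working it through.** **Inputs from G1 (2).** Difference of 1 face, SD 2.4, power 80%, alpha 0.05, stated n = 93. Sidedness is not stated; two-sided reproduces the figure.

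**Assumptions.** One face is one score point. The correlation ρ between a child's two ratings is not given, so a range is used.

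**1. Reproducing the 93.** The own-control design suggests a paired t-test, with

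SD of change = 2.4 × √(2(1 − ρ)).

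At ρ = 0 this is 2.4 × √2 = 3.39, and the paired t-test for a change of 1 point needs n = 93 (power 80.3%). The plan's figure is reproduced exactly.

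**2. How n depends on ρ under the same test.**

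| ρ | SD of change | n for 80% power | power with 93 |
|---|---|---|---|
| 0 | 3.39 | 93 | 80% |
| 0.3 | 2.84 | 66 | 92% |
| 0.5 | 2.40 | 48 | 98% |
| 0.7 | 1.86 | 30 | over 99% |

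Positive correlation makes 93 more than enough for this test. The table shows that an SD of change was needed and not given; it shows no shortfall.

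**3. What the planned analysis would deliver.** For a mean change in n children,

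95% half-width = t(0.975, n − 1) × SD of change / √n.

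For n = 93 and SD 3.39: 1.986 × 3.39 / √93 = 0.70. For n = 20 and SD 2.4: 2.093 × 2.4 / √20 = 1.12.

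| Children in the group | SD 2.4 (ρ = 0.5) | SD 3.39 (ρ = 0) |
|---|---|---|
| 93, all as one group | 0.49 | 0.70 |
| 46 per category | 0.71 | 1.01 |
| 30 per category | 0.90 | 1.27 |
| 20 per category | 1.12 | 1.59 |

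The category sizes are assumptions; the plan gives none. If the *a little* children come from the 93, then 46 per category is an even split (93 / 2 = 46.5) with nobody answering *much*.

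**4. When the half-width passes one point.** At SD 2.4, 25 children give 2.064 × 2.4 / √25 = 0.99 and 24 give 1.01. At SD 3.39, 47 children give 0.997 and 46 give 1.01. So a category with fewer than about 25 to 47 children has a half-width above one point.

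**5. Points per face.** If one face were 2 points (an assumption), the paired n would be 25 at ρ = 0 and 14 at ρ = 0.5. The half-widths in step 3 would be the same in points, so half as large in faces.

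**The case against.** The strongest reply is that nothing is miscalculated. The 93 reproduces, zero correlation is conservative, and the recommendation leaves 387 alone, so the power calculation may be read as a rough sizing device with no effect on conduct. The loss of precision also depends on category sizes that the documents do not give: with 40 children per category at ρ = 0.5 the half-width is 0.77, under one point, and if a face is 2 points then even 1.59 is less than a face. All of this stands. It limits the point to what G1 (2) claims, and does not make the 80% apply to G2 (3).

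A reader might also infer several stronger criticisms, which the documents do not support.

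- *The 93 can arise only from uncorrelated ratings.* A comparison of two independent groups with SD 2.4 gives 91 to 92 per group, also close to 93. It would need about 184 children in two groups, which this design does not have, but G1 (2) names no test.
- *The test would be circular, because the children are selected for having changed.* Selection on score forces the size of each change to be at least one face. It does not force the mean signed change away from zero, and G2 (3) selects on the child's answer rather than the score.
- *Zero correlation contradicts the reliability aim.* Objective 5 concerns children who rate their nausea as unchanged; the 93 are children who changed.
- *The plan's figures imply a much smaller SD among the third with nausea.* That gives about 1.39 only if every other child scores exactly 0, which the documents do not say. It would also narrow the intervals above.
- *The 93 gives no information on precision.* It implies about 0.70 points at ρ = 0 for a single group of 93. That figure is unstated and does not apply to the smaller groups.

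**Conclusion.** The point holds as a mismatch between the stated power and the planned analysis. On the plan's own calculation, the 80% would carry over to G2 (3) only if all 93 children gave an *a little* answer and were analysed as one group. G2 (3) plans no test, and nothing in the plan supports that count.

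In size, the half-width goes from 0.49 to 0.70 points for 93 in one group to 0.90 to 1.27 at 30 per category and 1.12 to 1.59 at 20. The last is about 2.3 times as wide as the first (1.59 / 0.70). This rests on the 2.4 from the cited study applying to these children, correlations of 0 to 0.5, and assumed category sizes. Whether the interval exceeds one face also depends on one face being one point.

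The check does not show that 93 is too small for the test it was computed for, or that 387 should change.

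**What to change.** In G1 (2), delete the 80% power claim for this aim. In its place:

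- State the expected number of children in *a little worse* and in *a little better*, with a range.
- State the expected 95% confidence half-width for the mean change in each category, as in step 3 of the working.
- Base it on an SD of change, shown over a range of within-child correlations, and not on the spread of single scores alone.
- Say how many score points one face represents.

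In G2 (3), add that the mean change in each category will be reported with its 95% confidence interval, so that the two sections match.

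Keep 387. The cost is one rewritten paragraph in G1 and one added sentence in G2, with no extra children or assessments. The stated figure will look less favourable than 80% power, but it will describe the analysis that is planned.

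### G1 (2): 387 recruits cover about 28% dropout from 279, not the stated 35%, and the 93 children sized are not the group that analysis (3) uses

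*Combined protocol and SAP*

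**What the plan says.** The total is given at the head of G1 as "Local: 387 Worldwide: 387". Its derivation is in G1 (2), on the minimum clinically relevant difference. For a one-face difference at 80% power and the 0.05 level, "we will need 93 subjects who had a change in their nausea scores". With PONV assumed in 33%, "a group size of 93 X3= 279 will be required to obtain 93 subjects with a change in nausea scores". The last step is "We plan to recruit 387 subjects to allow for a 35% dropout rate".

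G1 (1), on age-related ability to use the scale, follows the same pattern with a different rate: "This suggested a group size of 24 would be needed", and then "Allowing for a drop out rate of 20% we plan to recruit 28 in each of the 11 groups", which makes 308.

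The analysis that G1 (2) is meant to support is item (3) of G2. It calculates changes in BARF and VAS scores "for subjects who report their nausea as a little worse than before or a little better than before". Those answers come from the question in F2 where "patients will also be asked to rate their nausea on a 5 point Likert scale as" five options: much worse, a little worse, the same, a little better, much better.

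**The concern.** The dropout sentence is the only stated reason why the study recruits 387, and G1 then relies on that total for more than 80% power on the remaining aims. If 387 does not protect 279 against a 35% loss, the justification for the study size is false as written, and the plan misses its own target of 93 at its own dropout rate.

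The second issue is which children are counted. The power statement concerns children with a changed score. The minimal-difference estimate will come from children who choose one of the two *a little* answers. These groups overlap but are defined differently, and G1 has no step that converts one into the other.

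**Working it through.** **Inputs.** From G1 (2): 93 with a change, multiplier 3, 279 required, 387 recruited, 35% dropout, mean score 1.6 with SD 2.4, one-face difference, alpha 0.05, power 80%. From G1 (1): 24 needed, 28 recruited, 20% dropout, 11 age groups.

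**Reproducing the plan's figures**

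- The 93 can be recovered with a two-sided paired t-test, one face taken as one score unit, and uncorrelated scores. The SD of change is then 2.4 × √2 = 3.39, and n = 92.4, rounded up to 93. This reading is assumed and is not unique: a two-sample t-test at SD 2.4 needs 92 per group.
- 93 × 3 = 279, as stated. Using 33% instead of one third gives 93/0.33 = 281.8.
- The 387 is not recovered. Dividing by the retained fraction gives 279/0.65 = 429.2, so 430. Adding 35% on top gives 279 × 1.35 = 376.7, so 377. Starting from 282, the same two rules give 434 and 381.

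The fault therefore lies in the dropout step, not in the 93 or the 279.

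**What 387 delivers**

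- Dropout covered: 1 - 279/387 = 27.9% (27.2% starting from 281.8).
- Remaining at 35% loss: 387 × 0.65 = 251.6, about 252.
- With a change: 251.6/3 = 83.9, about 84, against 93 (84/93 = 0.90). With 33% instead of one third, 83. This takes loss to be unrelated to nausea.
- Extra recruits needed for 35%: 430 - 387 = 43.

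**Age groups, G1 (1)**

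- Needed for 20% loss: 24/0.80 = 30 per group. The add-on rule gives 24 × 1.2 = 28.8, so 28 does not follow from that either.
- Dropout covered by 28: 1 - 24/28 = 14.3%.
- Remaining at 20% loss: 28 × 0.80 = 22.4.

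**Effect on power, conditional on the paired reading above**

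Let r be the within-child correlation, so that the SD of change is 2.4 × √(2(1 - r)).

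| r | SD of change | Power at n = 84 |
|---|---|---|
| 0 | 3.39 | 76.1% (80.3% at n = 93) |
| 0.1 | 3.22 | 80.3% |
| 0.3 | 2.84 | 89.1% |
| 0.5 | 2.40 | 96.5% |

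Power at 84 reaches 80% at r of about 0.09.

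**Group sized against group analysed**

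- G1 (2) counts any child whose score changed, scaled by PONV incidence.
- Analysis (3) leaves out children who answer *much worse* or *much better*, although their scores may well have changed.
- Analysis (3) takes in a child who answers *a little better* but picks the same face, although that score did not change.
- The documents give no expected share of *a little* answers, so the size of the group, and even the direction of the difference, cannot be computed.

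**The case against.** The arithmetic is not open to dispute; the case on the other side concerns weight.

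- **Two dropout rates.** The plan gives 20% and 35% for the same children and does not define dropout. At 20%, 387 leaves 309.6 children and about 103 with a change, above 93. The in-hospital ratings may also lose fewer children than the mailed diary. This is fair, but the sentence in G1 (2) claims 35%, and at 35% it fails.
- **The add-on shortcut.** 387 exceeds the 377 that this shortcut gives. That may explain how the figure arose, but the shortcut does not protect 279 against a 35% loss and does not produce 387.
- **Small consequence.** A modest within-child correlation restores 80% power. Analysis (3) names no test, so it may be pure estimation; a confidence interval would then be about 5% wider (√(93/84) = 1.05). This stands, and it is why no claim of an underpowered study is made.
- **Age groups.** 387 spread evenly over 11 groups is about 35 each, or about 28 after 20% loss, so 24 could still be met. This limits the practical harm, but the plan does not say how the 79 children beyond 308 are allocated, and its sentence about 28 remains wrong. The 24 is also not confirmed: a two-sided two-sample t-test at d = 0.80 (assumed) needs 26 per group, and 24 gives 77%.
- **Group mismatch.** It is a separate point from the arithmetic, and its size is unknown. Both are true, but neither makes the 80% apply to analysis (3).

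**Conclusion.** The concern holds. The 35% allowance is incorrect: 387 covers 27.9%, and at 35% the expected number with a change is about 84, some 9 fewer than the plan requires. In G1 (1), 28 per group covers 14.3%, not 20%. These results need only the figures in G1 and, for the 84, loss unrelated to nausea.

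The effect on power is conditional: about 4 percentage points lost under zero correlation, and none below 80% once r is about 0.09 or more. The mismatch between the group sized and the group analysed is plain from the text, but its size cannot be derived. The sponsor should correct the plan; the error does not show that the study will fail.

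**What to change.** Keep 387 and correct the text.

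1. In G1 (2), replace the dropout sentence with: *387 recruits allow for about 28% dropout; at 35% dropout about 84 children with a change in nausea score are expected, not 93.*
2. After it, add: *The 93 counts children with a change in score. It is not the set used in analysis (3), so the 80% power does not apply directly to that estimate.*
3. In G1 (1), state that 28 per group allows for about 14% dropout.

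If power at 35% dropout is to be quoted, the sponsor should first state the test, the SD of change and the score value of one face that produced 93.

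The cost is text only. No further children are recruited and no procedure changes; the only loss is that the stated allowances become less favourable (28% instead of 35%, 14% instead of 20%). Keeping the 35% claim would instead mean 430 recruits, 43 more, and new totals at the head of G1; the correction does not require this.
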